1. Participants randomised to ApBM will consume significantly fewer standard drinks per week than participants in the minimal condition, as measured using self-report 4 weeks after commencing training (post-intervention; primary endpoint), and at 1-month and 3-month follow-ups (secondary endpoints).

Secondary outcomes:

2. Participants randomised to ApBM will show significantly larger declines, compared to those in the minimal condition, in past-week frequency of alcohol craving at post-intervention and follow-up assessments (relative to baseline craving frequency), as assessed by the frequency scale of the Craving Experience Questionnaire.
3. Participants randomised to ApBM will show significantly larger declines than those in the minimal condition in Severity of Dependence Scale scores at post-intervention and follow-up assessments (relative to baseline craving frequency).
4. Participants randomised to ApBM will show significantly larger declines than those in the minimal condition in Alcohol Use Disorders Identification Test (AUDIT) scores at the 3-month follow-up (relative to baseline scores).
5. Participants randomised to ApBM will have significantly fewer past-week heavy drinking days (HDDs, defined as ≥ 5 standard drinks in a day) than participants in the minimal

condition, as measured using self-report at post-intervention, 1-month, and 3-month follow-ups. Past-month HDDs will also be analysed post-intervention.

6. Participants randomised to ApBM will have significantly fewer past-month drinking days (i.e., days on which any alcohol is consumed) post-intervention and at 1- and 3-month follow-ups.
7. The proportion of participants reporting complete abstinence (i.e., 0 days on which any alcohol was consumed – both past week and past month will be analysed) will be significantly higher among participants in the ApBM than among those in the minimal condition at post-intervention and follow-up assessments.
8. Participants receiving ApBM will experience larger increases than those in the minimal condition in quality of life and health (assessed with 3 Australian Treatment Outcome Profile items) at post-intervention and follow-up assessments (relative to baseline).
9. There will be a significantly greater reduction in approach bias, as measured by the alcohol approach avoidance task, in participants assigned to the ApBM condition, compared to those in the minimal condition, between baseline and post-intervention.

Methods

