Alcohol craving: The Craving Experience Questionnaire frequency scale (CEQ-F) (May et al., 2014) will be used to measure the frequency of alcohol cravings over the past week. This is a 10-item scale, with each item rated on a scale of 0-10. Total scores are calculated based on the mean of individual items. Items can also be broken down into 3 subscales: "intensity" (3 items), "imagery" (4 items), and "intrusiveness" (3 items). The CEQ-F has an internal consistency of .94 and intercorrelations within each sub-scale range from .63-.73 (May et al., 2014).

In addition to the CEQ, we will also utilise a single-item visual analogue scale (VAS) to measure current intensity of alcohol craving immediately before and after each ApBM and AAT session. Participants will be asked "How strongly are you craving alcohol right now?", with a line displayed below the question and a slider that they can place between ends anchored with the words "not at all" on the left end and "extremely" on the right. A participants' placement of the slider will be converted to a number ranging from 0-100 for data storage. If participants provide a score of 90 or higher on the post-test VAS (i.e., immediately after completing an ApBM or AAT session), the app will prompt users with an additional support dialogue which links users to the National Alcohol and Other Drug Hotline and Counselling Online (www.counsellingonline.org.au).

Alcohol consumption: At baseline, participants will be asked to estimate the number of days on which they consumed alcohol out of the past 28 days and the number of standard drinks consumed on each day of the past week. To do this, they will be shown a calendar chart displaying the past 4 weeks, which will first be displayed with the most recent week in this period (i.e., 1-7 days ago) highlighted. For each day in this week, they will be asked to select a number ranging from 0-80 to indicate their estimate of how many standard drinks they consumed on that day in that week. Past-

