week standard drinks will therefore be calculated using the sum of values entered for each of the past 7 days, and past-week drinking days will be derived from the number of days in the past week for which the participant provided a non-zero value for standard drinks. Participants will then be shown the calendar chart with the previous week highlighted (8-14 days ago), where they will be asked to select a number ranging from 0-7 to indicate their estimate of how many days they consumed alcohol in that week. This will then be repeated with the previous week (15-21 days ago) and then the week previous to that (22-28 days ago). Baseline past-month drinking days will be calculated by summing past-week drinking days with the number of drinking days indicated for each of the 3 preceding weeks. The app will automatically prompt participants to repeat the past-week standard drinks assessment 7, 14, 21, and 28 days after they complete this baseline assessment, to provide complete standard drink and drinking days data for the intervention period. Drinking assessments at 1-month and 3-month follow-ups will be identical to the baseline assessment. The past-week drinking assessment closely resembles the computerised 7-day timeline follow-back assessment used by Simons, Wills, Emery, and Marks (2015), which showed 87% concordance with an objective transdermal measure of alcohol use in terms of drinking days.

Alcohol approach bias: At baseline and post-test, participants will be required to complete an adapted, irrelevant-feature, smartphone version of the alcohol approach-avoidance task (AAT) (R. W. Wiers, Rinck, Dictus, & van den Wildenberg, 2009). Each session of the AAT is immediately preceded and followed by the VAS craving measure. Participants in the minimal condition will also complete 3 additional sessions of the AAT at the end of week 1, week 2 and week 3 (directly after completing the weekly alcohol consumption questions at each timepoint) in order to maintain blinding.

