Secondary outcomes: Continuous outcome variables (CEQ, SDS, AUDIT, past-week HDDs, past-month drinking days, ATOP items, and approach bias) will be analysed in a similar manner to the primary analysis described above. In analyses of CEQ, SDS, past-week HDDs, past-month drinking days, and the 3 ATOP items, there will be 4 levels of time (baseline, post-intervention, 1-month, and 3-month follow-ups). Sensitivity analysis of past-week drinking days to control for the possible effect of past-week residential/inpatient treatment will be conducted as described for the primary outcome. Past-month drinking days will be expressed as a percentage of the total number of days on which a participant had the opportunity to drink (i.e., if a participant was in residential/inpatient treatment for 10 days at a certain time point, then for that time point, their past-month drinking days will be expressed as a proportion of the remaining 18 days on which they had the opportunity to drink), although data will be excluded at any time point where the participant did not have at least 14 days on which they had the opportunity to drink alcohol (i.e., if they were within residential/inpatient treatment on 15 or more days). For CEQ, secondary analyses will be conducted for each of its 3 subscales. Analyses of AUDIT scores will use 2 levels of time (baseline, 3-month follow-up). Approach bias analyses will also use 2 levels of time (baseline, post-intervention) and approach bias scores will be analysed separately for alcohol and positive images. As past-month HDDs can only be calculated at 1 time point (post-intervention), they will simply be compared between groups using a t-test post-intervention after converting scores to a proportion of days on which the participant had an opportunity to drink (as described for past-month drinking days). Proportions of groups reporting complete past-week and past-month abstinence will be compared between groups at post-intervention, 1-month follow-up, and 3-month follow-up using Pearson's chi-squared. uMARS "functionality", "aesthetics", and "subjective quality" scores, and participants' subjective ratings regarding AAT-App's effect on drinking and cravings will be explored within each group separately using descriptive data (e.g., mean, median, quartile cut-offs, percentages scoring above 3) to quantify typical ratings and proportions of participants providing favourable ratings. Where relevant, exploratory analyses will also compare mean scores of uMARS scales between groups using t-tests.

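### Past-month heavy drinking days are compared by an unadjusted t-test although related baseline drinking measures are collected, so this one secondary analysis gives up precision that covariate adjustment could recover

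*Combined protocol and SAP*

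**What the plan says.** Hypothesis 5 (Aims and Hypotheses) concerns heavy drinking days: "HDDs, defined as ≥ 5 standard drinks in a day". Its main measure is past-week HDDs at three time points. It then adds: "Past-month HDDs will also be analysed post-intervention".

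The Secondary outcomes part of Data Analysis gives the method for the added measure: "As past-month HDDs can only be calculated at 1 time point (post-intervention), they will simply be compared between groups using a t-test post-intervention". The count is first turned into a proportion of the days on which the participant could have drunk. No covariate is named.

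The Alcohol consumption part of Measures explains why there is only one time point. At baseline, participants report "the number of standard drinks consumed on each day of the past week". For each of the three earlier weeks they only "select a number ranging from 0-7 to indicate their estimate of how many days they consumed alcohol in that week". Daily drinks over a full 28 days exist only at post-intervention, where four weekly reports are put together.

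Two related baseline measures do exist. Past-week HDDs follow from the seven daily counts. The other is derived explicitly: "Baseline past-month drinking days will be calculated by summing past-week drinking days" and the drinking days of the three earlier weeks. The plan already models both with a baseline level: "In analyses of CEQ, SDS, past-week HDDs, past-month drinking days, and the 3 ATOP items, there will be 4 levels of time", the first of which is baseline.

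**The concern.** The lack of a past-month HDD baseline is a good reason not to fit a group-by-time model. It is not a reason to leave baseline drinking out altogether. A covariate need not be the same variable as the outcome or cover the same recall period; it only has to predict the outcome.

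This is the only planned comparison of heavy drinking over the whole four-week intervention. The post-intervention past-week HDD measure covers the last seven days, and the week-by-week model concerns standard drinks and is run only if a post-intervention difference is found.

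With a bare t-test, all between-person variation in how heavily people drank at entry stays in the error term. Randomisation is stratified by site only, so nothing in the design balances baseline heavy drinking beyond chance, and the estimate cannot be adjusted for an imbalance that does occur.

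**Working it through.** **The plan's own figure.** The Participants section gives 178 participants for 90% power at a partial eta squared of .01 with four repeated measures. Take f² = .01/.99 = 0.0101, a correlation of 0.5 between repeated measures (not stated; assumed), and noncentrality = 178 × 4 × 0.0101 / (1 − 0.5) = 14.4 on 3 and 3 × (178 − 2) = 528 degrees of freedom. Power is then 90.2%, so the figure reproduces. At assumed correlations of 0.3 and 0.7 it would be 77.0% and 99.1%. This calculation is for weekly standard drinks. The documents give no power figure for past-month HDDs.

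**Inputs for this test.**
- Alpha .05 (Data Analysis), taken as two-sided.
- 1:1 allocation (Design & Setting).
- 89 per arm, which is 178/2. This is an assumption: 178 belongs to the primary analysis, the recruitment target is at least 300, and no analysed number is stated for past-month HDDs.
- rho, the correlation of the baseline covariates with the outcome (the multiple correlation when there are two). Not given; taken as 0.1 to 0.7.
- Effect size d, not given. It is set to the value that the t-test detects with 80% power.

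**Unadjusted t-test.** d = (1.960 + 0.842) × √(2/89) = 2.802 × 0.1499 = 0.42.

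**Adjusted model.** The residual variance is multiplied by 1 − rho², so the standardised signal rises from 2.802 to 2.802/√(1 − rho²), and power is Φ(2.802/√(1 − rho²) − 1.960). For rho = 0.5: 2.802/0.866 = 3.235; 3.235 − 1.960 = 1.275; power is 89.9%.

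| rho | 1 − rho² | CI width relative to t-test | power at d = 0.42 | d detectable at 80% | total N for d = 0.42 at 80% |
|---|---|---|---|---|---|
| 0.1 | 0.99 | 0.995 | 80.4% | 0.418 | 178 |
| 0.3 | 0.91 | 0.954 | 83.6% | 0.401 | 162 |
| 0.5 | 0.75 | 0.866 | 89.9% | 0.364 | 134 |
| 0.7 | 0.51 | 0.714 | 97.5% | 0.300 | 92 |

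Noncentral-t calculations agree within half a percentage point. A second covariate costs one more degree of freedom and leaves power unchanged to three decimals at rho of 0.3, 0.5 and 0.7. A gain of 5 points from 80% needs rho of about 0.355.

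**A smaller effect.** For an effect that the t-test detects with 60% power (d = 0.33), adjustment gives 64.1%, 72.4% and 87.3% at rho of 0.3, 0.5 and 0.7.

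**The case against.** **The t-test is not out of line with the rest of the plan.** A reader might infer that past-month HDDs are singled out for unadjusted testing. The documents do not support that. The primary outcome has planned t-tests at each time point, and the other continuous outcomes are to be handled similarly. The narrower difference stands: the other continuous drinking outcomes also have a mixed model with baseline as a time level, and this one has no such model.

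**The t-test is valid.** A reader might infer bias. Under randomisation there is none: the type I error rate and the confidence interval already allow for chance imbalance. Only efficiency and conditional adjustment are at stake, in a measure that hypothesis 5 adds to past-week HDDs.

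**The size is assumed.** Neither rho, d nor the analysed number is in the documents, and starting from 80% power is a choice. The covariates may predict weakly: participants are in treatment, so their drinking may be changing, and an inpatient stay before the final pre-screening week is allowed. All of this stands. A reader might take the rise from 80% to 90% as the plan's loss, but it is only the rho = 0.5 row.

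**The baseline is reported after allocation.** Under Procedure, the access code is sent and the app is opened first. Active participants watch an animation on how the training works, controls read different text, and only then do both report baseline drinking. Adjusting for that report could carry an arm effect into the estimate. This is a fair caution, but the plan already uses the same report as baseline in its primary and secondary models. It calls for the unadjusted result beside the adjusted one and does not defeat the adjustment.

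**Conclusion.** The concern holds as a minor matter of efficiency. The reason given for the t-test excludes a repeated-measures model only, and suitable covariates are already in the dataset. The loss is confined to one secondary analysis and consists of precision and the ability to adjust for a chance imbalance.

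Its size cannot be read from the documents. On the assumptions above, the gain from adjustment is negligible at rho = 0.1, about 4 points at 0.3, about 10 at 0.5 and about 17 at 0.7. The direction is secure for any non-trivial correlation; the amount is illustrative.

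**What to change.** Before unblinding, amend the sentence on past-month HDDs under Secondary outcomes as follows.

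- **Main analysis:** a linear model of the post-intervention past-month HDD proportion on group, baseline past-week HDDs and baseline percentage of past-month drinking days, with robust standard errors. Report the adjusted mean difference with its 95% confidence interval.
- **Missing covariates:** keep participants whose baseline covariate is missing, for example where the plan's 14-opportunity-day rule removes the drinking-day percentage. Use simple baseline imputation or a missing indicator, and name which one in advance.
- **Unadjusted result:** always report the t-test alongside, because the in-app baseline follows allocation and arm-specific onboarding.
- **Optional sensitivity model:** adjust instead for AUDIT, SDS or CEQ-F, which are collected before the access code is sent.

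The cost is a few sentences in the analysis plan and one extra model. No new data are needed. Adjustment does not recover participants who lack the weekly reports from which the 28-day count is built.

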Design & Setting: We will conduct a double-blind, randomised, parallel-group controlled superiority trial with alcohol treatment outpatients at 6 AOD treatment services in Melbourne, Victoria. Participants will be randomised to one of 2 groups with a 1:1 allocation ratio. Both participants and researchers completing the follow-up interviews will be unaware (blinded) of the condition to which they have been randomly allocated.

Participants: We aim to recruit at least 300 participants receiving outpatient interventions for alcohol use disorder at the participating services. To be eligible, participants must, at the time of the screening interview:

- Be aged 18+
- Own an Android or iOS smartphone with an Australian mobile number
- Be currently accessing outpatient treatment for alcohol problems. (There is no requirement that alcohol be the *only* substance for which they are seeking treatment, and as such participants with multiple drugs of concern are eligible as long as alcohol is one of the drugs of concern for the current episode of treatment.)
- Have an Alcohol Use Disorders Identification Test (AUDIT) score of at least 8
- Not have been in residential rehabilitation within the past 4 weeks.
- Not have been in any form of inpatient treatment (e.g. hospital or residential withdrawal treatment) within the past week.
- Not entering inpatient/residential treatment within the next month.

The target sample size was determined based on practical considerations (likely recruitment rate, time available for recruitment), as there was little prior basis to estimate likely effect size of a personalised ApBM smartphone app in an outpatient client population. Nevertheless, a calculation conducted in GPower 3.1 suggested that the primary analysis (across 4 repeated measures) would have 90% power to detect a small time x group interaction effect size (partial eta squared of .01) with a sample of 178 participants (i.e., 59% retention at follow-ups). If recruitment proceeds quickly enough, we will aim to recruit more than 300 participants, to allow for increased statistical power in case attrition is larger than expected.

Measures:

Demographic information: Participants will be asked to enter their gender, the AOD service where they were recruited from, the date they began the current episode of treatment they are receiving from that service, and drugs of concern, in an online survey hosted on Qualtrics.

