variable size (ranging from 2-6). As such, randomisation will be stratified by site. The app developers (ANT Development Studios Ltd.) will provide the data scientist with two lists of app access codes which will direct participants to either the intervention or minimal version of AAT-App when they first download and open the app. Using these lists and the randomisation sequence, the data scientist will generate a separate spreadsheet of access codes for each site (based on the site-stratified randomisation sequence). Researchers will send these codes to participants as they are recruited from each respective site. Researchers involved in recruitment will only have access to a spreadsheet displaying a single list of codes to be sent to participants at each respective site, while the randomisation sequence will be stored in a password-protected file provided to the trial statistician and to one research officer who will remain unblinded to assist with coordinating qualitative interviews. Neither the randomisation file, nor its password will be provided to any other staff (including the principal investigator, [name], and research officer, [name]) involved in recruitment or in pursuing follow-ups or quantitative data management until all data analysis is complete.

Intervention: Prior to commencing the intervention, participants will be prompted to select 6 alcohol-related pictures that represent the drinks they most frequently consume. Participants can either select from their own photographs stored on their phone, take photographs of alcoholic beverages using the app, or select pictures from a library of 67 alcohol-related images chosen to represent a broad range of alcoholic beverages commonly consumed in Australia. Participants will then be prompted to select 6 pictures that “represent your goals and motivations”. Again, participants can either select their own photographs, take photographs, or select pictures from a library of 68 pictures representing a range of healthy activities or positive goals and sources of pleasure (including family or friends enjoying time together; financial success; employment; exercise, sports, and recreational activities; healthy foods; pets; travel and holidays) which do not contain any depictions of alcohol. If participants take/use their own photographs, they will be reminded to ensure that positive images do not contain depictions of alcohol.

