Participants will be required to indicate that they have read and understood the information and consent to participate. This will result in the remaining baseline questionnaires being displayed including items assessing gender, which AOD treatment service the participant is attending, type(s) of treatment being accessed, drugs of concern, date of commencement of the current episode of treatment, treatment goal (abstinence or moderation), SDS, CEQ-F, and ATOP quality of life items. They will also be required to enter their smartphone number, and are encouraged to enter additional contact details (e.g., name, email, other phone numbers, and postal address) to assist with ensuring follow-ups are completed, although this is not required.

Completing the Qualtrics survey will result in an email being automatically sent to researchers, who will access the list of access codes, select the first unused code, and send the download link and access code to the participant via SMS. The researcher will record which access code was sent to which phone number. Once participants have downloaded the app, they will be prompted to enter the access code, thus resulting in either the ApBM or minimal version of the app being installed on their phone. Participants in the active condition will view a short introductory animation explaining how the ApBM intervention works, while participants in the minimal condition will be onboarded through written text that ensures blinding is maintained (see details provided above). Participants will then be required to complete the baseline alcohol consumption questions, before completing the pre-training VAS craving measure, the AAT, and the post-training VAS craving measure. Participants in the active condition will then proceed to the image selection feature, where they will be prompted to upload or select 6 alcohol-related images and 6 positive images to be used in the ApBM training task. These participants will then complete the pre-training VAS craving measure, their first session of the ApBM task, and the post-training VAS craving measure.

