Audio-recorded qualitative interviews and verbal consent will be stored as .mp4 files on a secure Google drive hosted by Monash University, access to which will be restricted to project personnel (but which will not be made accessible to blinded quantitative data collectors until data collection is complete). The .mp4 files will be securely transferred to Pacific Transcription, a trusted transcription service provider that is frequently used by Monash University and Turning Point. To preserve participant anonymity the recording of verbal consent (where the participant states their full name and is also asked about their phone number) will be separated from the rest of the file and stored separately, while the main interview file will be labelled with a participant number (this number will be the same as the participant access code used to access the app, allowing baseline demographic data to be matched to qualitative interview data), not their name. Transcripts returned by Pacific Transcription will be stored as .docx files on the secure Google drive until data collection is complete. Once data collection is complete and blinding no longer required, these files will be stored in the project folder on the Turning Point Clinical Research Drive. They will be deleted from the Google Drive once analysis and publication is complete, and stored for at least 7 years following publication of the last paper arising from this study, or 7 years after the final report to the ethics committee, or 7 years after final reporting of outcomes on the clinical trials registry, whichever occurs latest.

Data Analysis

Statistical significance will be ascertained using $\alpha=.05$. Any participants who commenced at least 1 session of ApBM (if in the ApBM condition) or AAT (if in the minimal control condition) will be included in the analysis population.

Primary outcome: A linear mixed-effects model (LMM) will be used to compare change in mean standard drinks consumed per week between groups across 4 time points (baseline, post-intervention, 1-month follow-up, and 3-month follow-up). This model will test the main effects of time and group and (most crucially for determining efficacy) the group x time interaction. Planned follow-up comparisons between groups at post-intervention, 1-month follow-up, and 3-month

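### Abstinence is compared by separate unadjusted chi-squared tests that leave out the site stratification and recorded prognostic baseline data, which gives up some power

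*Combined protocol and SAP*

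**What the plan says.** Aims and Hypotheses (hypothesis 7) predicts a higher proportion completely abstinent under ApBM after the intervention and at follow-up, and adds that "both past week and past month will be analysed". Data Analysis, Secondary outcomes, compares these proportions "at post-intervention, 1-month follow-up, and 3-month follow-up using Pearson's chi-squared", naming no covariate or stratum. The linear mixed model is kept for "Continuous outcome variables (CEQ, SDS, AUDIT, past-week HDDs, past-month drinking days, ATOP items, and approach bias"), a list without abstinence. The general rule is "Statistical significance will be ascertained using $\alpha=.05"; sidedness is not stated.

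Three relevant baseline items exist and do not enter this test:

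- **Site.** Randomisation and blinding of allocation: "As such, randomisation will be stratified by site" (six sites).
- **Treatment goal.** Procedure: the baseline survey, completed before the access code is sent, records "treatment goal (abstinence or moderation").
- **Baseline drinking.** Measures, Alcohol consumption: daily standard drinks for the past week and drinking days over 28 days. Procedure places these questions in the app, after the access code has fixed the arm and after active participants have seen the introductory animation.

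The section does not say how a missing abstinence report is handled.

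**The concern.** Drinking at entry and the goal of treatment are obvious candidate predictors of later abstinence. Entry requires an AUDIT score of at least 8 but no minimum recent consumption, so a participant could already be abstinent in the week before baseline. A crude proportion cannot separate such a person from one who stopped during the trial. Randomisation balances this on average, so the test is valid, but the prognostic variation stays in the comparison as noise.

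Two other things are set aside. If abstinence differs between sites, a test that ignores the stratification tends to be conservative. And three separate tests per window do not use the correlation between a participant's reports at different visits, which the mixed model does use for the continuous outcomes.

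What is at stake is the chance of detecting a true difference on hypothesis 7.

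**Working it through.** **1. The plan's own figure.** The Participants section claims "90% power to detect a small time x group interaction effect size (partial eta squared of .01"). The number it gives for this is 178, which it equates to 59% retention. For a repeated-measures interaction with 2 groups and 4 measures, f² = 0.01/0.99 = 0.0101. With correlation 0.5 between measures and no sphericity correction (neither is stated), the noncentrality is f² × N × 4/(1 − 0.5) = 0.0101 × 178 × 8 = 14.4, on 3 and 3 × 176 = 528 degrees of freedom. Power is 0.902, so 178 reproduces, and 178/300 = 59.3%. At correlation 0.3 or 0.7 the required number would be 248 or 108. No figure is given for abstinence.

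**2. Power of the planned test (abstinence rates assumed).** With n per arm, p̄ the mean of p₁ and p₂, and two-sided 5%:

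power = Φ{(|p₂ − p₁| − 1.96 √[2p̄(1 − p̄)/n]) / √[(p₁(1 − p₁) + p₂(1 − p₂))/n]}

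Example, 20% vs 35%, n = 89: (0.150 − 1.96 × 0.0669)/0.0660 = 0.285, so power is 61%.

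| Control vs active | 89 per arm | 150 per arm |
|---|---|---|
| 10% vs 20% | 46% | 68% |
| 20% vs 30% | 34% | 52% |
| 20% vs 35% | 61% | 83% |
| 30% vs 45% | 54% | 77% |

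**3. Gain from adjustment (rates and prognostic strength assumed).** 2,000 simulated trials per cell, 178 participants, no dropout: chi-squared against logistic regression adjusted for one baseline score. Each cell shows unadjusted → adjusted power.

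| Log-odds per SD of score | 10% vs 20% | 20% vs 35% | 30% vs 45% | Gain, points |
|---|---|---|---|---|
| 0.5 (weak) | 47 → 47% | 60 → 62% | 54 → 56% | 0-2 |
| 1.0 (moderate) | 44 → 48% | 60 → 67% | 55 → 62% | 4-7 |
| 1.5 (strong) | 44 → 52% | 62 → 74% | 56 → 67% | 8-12 |
| 2.0 (very strong) | 44 → 59% | 63 → 80% | 55.4 → 74.7% | 15-19 |

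With all 300 observed, the moderate case goes from 83.8% to 88.1% (20% vs 35%) and from 74.0% to 82.6% (30% vs 45%). These runs cover covariate adjustment at one visit; the full repeated-measures model was not simulated.

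**4. Attrition, with no true effect.** 300 randomised, about 59% retained, assumed abstinence 20% or 30%, log-odds 0.5 to 1.5 per SD.

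| Retention depends on | Chi-squared: bias; type I error | Adjusted: bias; type I error |
|---|---|---|
| nothing, or prognosis equally in both arms | about 0; 4-6% | about 0; 4-6% |
| prognosis, differently by arm | 1-9 points; 6-25% | about 0; 4-6% |

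The adjusted analysis succeeds in the second row because dropout was generated from the covariate in the model. A separate run made retention depend on the outcome itself in one arm only: 80% of abstainers and 52% of drinkers retained there, 59% in the other arm, true abstinence 25% in both. Adjusting for baseline abstinence and goal (odds ratios 4 and 3, then 8 and 4) reduced the false difference only from 8.9 to 7.9 points, and from 9.0 to 7.3. Type I error stayed at 21-22%, against 26-27% for chi-squared.

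**The case against.** Chi-squared on randomised proportions is conventional, valid and easily read. Abstinence is one of eight secondary hypotheses. Past-month drinking days, of which past-month abstinence is a dichotomy, already has a four-time-point mixed model. Goal and site are not named in the primary model either, and its comparisons at single time points are t-tests. The gain is small unless predictors are strong, and 178 is the number required, not the 300 targeted. All of this stands. It limits the point to an inexpensive improvement, but does not explain why recorded prognostic data should be left out.

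The timing of baseline drinking is also a fair objection. The questions concern the period before allocation, but the answers are given afterwards, and only active participants have by then seen an explanation of ApBM. Adjusting for that report is therefore not free of risk.

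A reader might go further and infer that chi-squared leaves attrition bias which the model would remove. The documents do not support that. Bias in the null comparison needs dropout related to drinking differently by arm. Nothing in the plan shows this, and the Introduction describes a control condition designed partly to limit differential dropout. An example can be built in which equal true rates of 25% appear as 34% vs 25%: 0.25 × 0.80/(0.25 × 0.80 + 0.75 × 0.52) = 0.339. It makes retention depend on the unobserved outcome in one arm, which the model does not repair (step 4). Analysis of responders only is the natural reading of the plan but is not written. That many participants have an abstinence goal, or that abstainers respond more often, has no source in the documents.

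**Conclusion.** The point holds as a modest loss of efficiency. The planned tests ignore the stratification factor and recorded baseline predictors. At 178 participants, adjustment is worth about 0-2 points of power with weak predictors, 4-7 with moderate ones, and more only with strong ones. All of these sizes rest on assumed abstinence rates and prognostic strengths, and the documents cannot narrow them. The case for changing the plan is precision. Protection against attrition bias is a conditional benefit: it applies only if dropout is explained by the modelled covariates and earlier reports. The primary conclusion is unaffected.

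**What to change.** In Data Analysis, Secondary outcomes, make the main abstinence analysis, for each window, a mixed-effects logistic model over post-intervention, 1 month and 3 months. Include a participant random intercept, group, time, group x time, site, treatment goal and baseline drinking days. From it, report standardised (marginal) proportions and risk differences by group at each time point, averaging over the covariates and the random effect. Keep chi-squared as a descriptive check.

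Add a sensitivity analysis adjusting only for covariates recorded before allocation: site, treatment goal and the screening AUDIT. State that the model relies on outcomes being missing at random given the modelled covariates and earlier reports, and does not correct dropout that depends on the unobserved outcome.

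The cost is wording only, since every variable is already collected. The downside is that model estimates must be converted to proportions for reporting.
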